#### **11.4.3 Analysis of safety endpoints**

No formal statistical tests will be performed on safety endpoints analysis.

Safety endpoints are presented in [Section 9.2](#). These analyses will be based on the Safety Population as defined in [Section 11.3.2](#). Patients will be analyzed for safety analyses according to the treatment actually received. All safety analyses will be performed on the safety population using the following common rules:

The following definitions will be applied to laboratory parameters and vital signs:

- Potentially clinically significant abnormality (PCSA) values for clinical laboratory tests and vital signs will be defined as abnormal values considered medically important by the Sponsor's Global Pharmacovigilance and Epidemiology department and in effect at the time of the final SAP approval. The PCSA criteria for parameters not cited in the protocol as safety parameters will not be analyzed.
- The PCSA criteria will determine which patients had at least 1 PCSA during the TEAE Period, taking into account all evaluations performed during the TEAE Period, including unscheduled or repeated evaluations. The number of all such patients will be the numerator for the treatment-emergent PCSA percentage.

The "observation periods" defined in [Section 9.2](#) are applicable for classification of AEs and determination of PCSA values on the TEAE period.

##### **11.4.3.1 Analysis of the key and other safety endpoints for BMD**

Analysis of percent change from Baseline in BMD to Week 26, Week 52, and Week 104 will be performed on the safety population, using BMD measurements obtained during the study, including those obtained after IMP discontinuation or introduction of rescue therapy. No statistical significance tests will be performed.

Analysis of the key secondary safety endpoint of percent change from Baseline to Week 26 in BMD will be performed using an ANCOVA model. To compare sotagliflozin 400 mg and 200 mg versus placebo, the model will include treatment groups (sotagliflozin 400 mg, sotagliflozin 200 mg, placebo), randomization strata of HbA1c ( $\leq 8.5\%$ ,  $> 8.5\%$ ), sex (male, female), and country as fixed effects, and Baseline BMD value as a covariate, providing the adjusted LS mean percent change from Baseline to Week 26 for each treatment group, as well as the between-group difference (comparing each sotagliflozin group vs placebo group) and the 95% CI for the difference.

The last-observation-carried-forward (LOCF) approach will be applied for the missing data imputation of the key safety endpoint of percent change in BMD from Baseline to Week 26. As the Week 26 Visit is the first post-Baseline scheduled visit for BMD measurement, if a patient withdraws early from the study before Week 26, the BMD measurement collected at the withdrawal visit will be used carrying forward to Week 26 in analysis.

The percent change from Baseline to Week 52 (or Week 104) in BMD will be analyzed using a mixed-effect model with repeated measures (MMRM). The MMRM model will include treatment groups (sotagliflozin 400 mg, sotagliflozin 200 mg, placebo), randomization strata of HbA1c ( $\leq 8.5\%$ ,  $> 8.5\%$ ), sex (male, female), visit, treatment-by-visit interaction, and country as fixed effects, and Baseline BMD value-by-visit interaction as covariate, providing the adjusted LS mean percent change from Baseline to Week 52 (or Week 104) for each treatment group, as well as the between-group difference (comparing each sotagliflozin group vs placebo group) and the 95% CI for the difference.

Descriptive analyses will be performed on safety endpoints of BMD change to summarize the treatment effects across subgroups defined by the following Baseline or Screening factors:

- Age group ( $< 65$  years,  $\geq 65$  years).
- Duration of T2D ( $< 10$  years,  $\geq 10$  years).
- Sex (male, female).
- Baseline BMI level ( $< 25$ ; 25 to  $< 35$ ;  $\geq 35$  kg/m^2).
- Baseline eGFR ( $< 45$ ; 45 to  $< 60$ ;  $\geq 60$  mL/min/1.73 m^2).

Summary statistics (observed values, observed percent change from Baseline) at scheduled visits will be provided for each treatment group. The summary will include the number of observations, mean, SD, SE, minimum, median, and maximum. Graphical presentations will also be used to examine trends over time using mean values ( $\pm$ SE), mean changes from baseline ( $\pm$ SE), and mean percent change from baseline at each of the scheduled visits (using OC).

Sensitivity analyses might be performed to assess the impact of missing data if needed.

#### **11.4.3.2 Analysis of adverse events**

**Pretreatment AEs** are AEs that developed or worsened or became serious during the pretreatment period.

**Treatment-emergent AEs** are AEs that developed or worsened (according to the Investigator's opinion) or became serious during the TEAE period.

**Post-treatment AEs** are AEs that developed or worsened or became serious during the post-treatment period.

The primary focus of AE reporting in the CSR will be on TEAEs. Pre- and post-treatment AEs will be described separately.

### **All adverse events**

Adverse event incidence tables will present by system organ class (SOC) (sorted by internationally agreed order), high level group term (HLGT), high level term (HLT), and preferred term (PT) sorted in alphabetical order for each treatment group, the number (N), and percentage (%) of patients experiencing an AE. Multiple occurrences of the same event in the same patient will be counted only once in the tables within a treatment Phase. The denominator for computation of percentages is the safety population within each treatment group.

Summaries of all TEAEs in each treatment group will include:

- The overview of AEs, summarizing number (%) of patients with any:
  - TEAE.
  - Serious TEAE.
  - TEAE leading to death.
  - TEAE leading to permanent treatment discontinuation.
- The number (n) and percentage (%) of patients with at least one TEAE by primary SOC, HLGT, HLT, and PT.
- Summary of TEAEs by maximal severity (severe, moderate, mild), presented by primary SOC and PT.
- Summary of TEAEs possibly related to IMP, presented by primary SOC, HLGT, HLT, and PT.

A detailed listing of TEAE summaries will be provided in the SAP.

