Based on evaluation of the cumulative safety data for the sotagliflozin clinical program, genital infections are monitored closely as an important identified risk. However, reports of these events have been infrequent and have responded to standard treatment. Diabetes ketoacidosis has been reported with treatment with other SGLT2 inhibitors and for this reason is identified as a potential risk. As of December 2016, two SAEs of DKA were reported in 2 patients with T1D and receiving sotagliflozin. Both SAEs were considered by the investigator to be due to insulin pump failure and unrelated to study treatment. Other potential risks are defined based on either their potential link to sotagliflozin mechanism of action, or because occurred during treatment with other SGLT2 inhibitor drugs. These potential risks have not been found to be in imbalance in sotagliflozin clinical trials, but will be also monitored in the study as events of special interest (EOSI), including urinary tract infections (UTI), diarrhea, pancreatitis, CV and renal events, drug-induced liver injuries (DILI), malignancies, volume depletion, and amputation. Evaluation of bone fractures will be of special relevance in this study as it includes a population of patients at increased risk for fractures.

Risks specific to this study are associated with the placebo-controlled design and long treatment duration. There is potential risk of insufficient glucose control, especially in the placebo arm during this 2-year study. Investigators will monitor regularly the glucose control at regular study visits by reviewing patients' fasting self-monitored blood glucose (SMBG) in conjunction with central laboratory alerts for FPG and HbA1c programmed based on progressively stricter hyperglycemic thresholds. In case patients develop uncontrolled hyperglycemia during the study, Investigators will provide open-label antidiabetes rescue treatment and continue monitoring the patients as part of the study. Additionally, investigators can also provide rescue treatment at any time if medically indicated.

Patients may experience some discomfort associated with study procedures, such as blood draws, electrocardiogram (ECG), and fingersticks for SMBG. The Investigators will monitor for any possible occurrence of side effects related to these procedures.

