#### **10.4.1.4 Events of special Interest**

An EOSI is a serious or nonserious AE of scientific and medical concern specific to the Sponsor's product or program, for which ongoing monitoring may be appropriate. Such events may require further investigation to characterize and understand them. These events should be reported on the specific eCRF page (where applicable) and will only qualify for expedited reporting when serious (fulfilling SAE criteria).

The EOSIs for this study are:

- MACE (CV death, MI, or stroke) and other specific CV events (eg, hospitalization for heart failure).
- Severe hypoglycemia (see [Section 10.6.1](#)).
- Genital mycotic infections (to include vulvovaginal candidiasis in females and candida balanitis in males).
- UTIs.
- Clinically relevant volume depletion and events related/possibly related to volume depletion.
- Diarrhea.
- Pancreatitis.
- Bone fractures.
- Venous thrombotic events to include deep venous thrombosis and thromboembolism (to include pulmonary embolism).
- DKA.
- Renal events to include 50% decline in eGFR, end stage kidney disease, renal death.
- Malignancies of special interest (breast, bladder, renal cell, Leydig cell, pancreatic, prostate, and thyroid carcinoma).
- TEAEs leading to amputation.

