#### **11.4.3.4 Analyses of events of special interest**

The number (n) and percentage (%) of patients with each EOSI event will be summarized by treatment group. All events reported by the Investigators on the AE forms for AESI/EOSI will be listed along with the adjudication outcome (if applicable).

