- For quantitative safety parameters based on central laboratory/reading measurements, descriptive statistics will be used to summarize results and change from Baseline values by visit and treatment group for the 104-week entire treatment period. Summaries will include the last on-treatment value. The last on-treatment value is commonly defined as the value collected at the same day/time of the last administration of IMP for the 104-week entire treatment period. If this value is missing, the last on-treatment value will be the closest value prior to the last administration of IMP during the 104-week entire treatment period.
- The analysis of the safety variables will be essentially descriptive and no systematic testing is planned. Relative risks versus placebo and their 95% confidence intervals may be provided, if relevant.
- Selected safety analyses will be summarized by age, gender, racial subgroups, and any pertinent subgroups (see details in [Section 2.4.5.3](#) and [Section 2.4.5.4](#)).

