- All treatment-emergent adverse event by primary SOC, HLGT, HLT, and PT, showing number (%) of patients with at least 1 treatment-emergent adverse event sorted by the SOC internationally agreed order. The other levels (HLGT, HLT, PT) will be presented in alphabetical order.
- Number (%) of patients experiencing TEAE(s) presented by PT, sorted by decreasing incidence of PT in the sotagliflozin 400 mg group.
- All treatment-emergent adverse events by primary SOC and PT, showing the number (%) of patients with at least 1 treatment-emergent adverse event, sorted by the internationally

agreed SOC order and by decreasing incidence of PTs within each SOC in the sotagliflozin 400 mg group. This sorting order will be applied to all similar other tables, unless otherwise specified.

- All treatment-emergent adverse events regardless of relationship and related to IMP by primary SOC, HLGT, HLT and PT, showing the number (%) of patients with at least 1 treatment-emergent adverse event, sorted by the internationally agreed SOC order. The other levels (HLGT, HLT, PT) will be presented in alphabetical order.
- All treatment-emergent adverse events by maximal severity, presented by primary SOC and PT, showing the number (%) of patients with at least 1 treatment-emergent adverse event by severity (ie, mild, moderate, or severe), sorted by the sorting order defined above.
- Common TEAEs (PTs with incidence $\geq 2\%$ in any treatment group) by primary SOC, HLGT, HLT and PT, sorted by the internationally agreed SOC order. The other levels (HLGT, HLT, PT) will be presented in alphabetical order.
- Common TEAEs (PTs with incidence $\geq 2\%$ in any treatment group) will be provided as appropriate by primary SOC and PT and by demographic factors including gender, age group (≥ 55 to < 65 , ≥ 65 years), race (White, Black or African American, Asian, other), baseline SBP category (< 130 , ≥ 130 mmHg), and baseline eGFR category (≥ 30 to < 60 mL/min/1.73m² [Moderate decrease in GFR], ≥ 60 to < 90 mL/min/1.73m² [Mild decrease in GFR], and ≥ 90 mL/min/1.73m² [Normal]), prior antidiabetic medication [Insulin (alone or with other antihyperglycemic agents), SU and/or glinide (alone or with other non-insulin antihyperglycemic agents), Other (non-insulin antihyperglycemic agents except SU, and glinide)]. SOC will be sorted by the internationally agreed order and the PT by decreasing incidence within each SOC in the sotagliflozin 400 mg group, as described above.

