For the EOSI renal events where selected events are adjudicated, the number (%) of patients with any renal events identified in [Table 3](#) in [Section 2.1.4.2](#) will be summarized by treatment group.

The following renal events will be listed along with the adjudication outcome if applicable, including events,

- i. Recorded in eCRF “GFR decrease”.
- ii. Recorded in eCRF “Renal Event – Dialysis”.
- iii. Identified as “Renal transplant” in eCRF “Other procedure”, where adjudication is not required.

Renal death will be part of all deaths specified above.

Other EOSIs

For EOSIs that are not adjudicated, the number (%) of patients with at least one event will be summarized by treatment group and by PT (as identified in [Table 3](#) in [Section 2.1.4.2](#)).

Severe hypoglycemia will be included in the summary of hypoglycemia (See [Section 2.4.5.1](#)).

AE leading to an amputation is described in the section below.

Analysis of Amputation:

The number (%) of patients with amputation will be summarized by treatment group and by PT and LLT during the study (ie, regardless of on- or post-treatment). Amputation is a procedure recorded in eCRF form “Other Procedures related to Amputation”. Patients who had a procedure related to amputation will be listed.

The number (%) of patients with an “AE leading to an amputation” will be summarized by treatment group and by PT. The “AE leading to an amputation” is determined by the AE identifier recorded in eCRF “Other Procedures related to Amputation” when “AE correction” is chosen as the reason for the amputation procedure.

In addition, the number (%) of patients with an “AE potentially leading to an amputation” will be summarized by treatment group and by PT (as identified in [Table 2](#) in [Section 2.1.4.2](#); these PTs in [Table 2](#) were requested by the European Medicines Agency/ Pharmacovigilance Risk Assessment Committee[EMA/PRAC] Assessment Report 9 February 2017). The associated list will be provided as well, with patients who had an amputation procedure flagged. “AE potentially leading to amputation” represents the condition that commonly precedes amputation procedure, but not in all cases an amputation has occurred (as per the EMA/PRAC request).

Analysis of pretreatment and posttreatment adverse events

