Proportion of patients requiring rescue for hyperglycemia during the 104 weeks	ITT	Summary statistics	No	No	KM plot , List of patients rescued

Endpoint	Analysis population	Primary analysis	Supportive analysis	Subgroup analysis	Other analyses
Other safety endpoints					
BMD (lumbar spine, total hip, and femoral neck): Percent change from Baseline at Weeks 52 & 104	Safety	ANCOVA (with missing values imputed using retrieved dropouts method or by ANCOVA (MMRM) Trt, randomization strata (HbA1c, Sex), visit, trt-by-visit interaction and country as fixed effects, and Baseline BMD value-by-visit interaction as a covariate	ANCOVA (MMRM)	No	Summary statistics for observed values, changes and percent changes from Baseline by visit. Graphical presentations for mean percent changes from Baseline (\pm SE) and mean values (\pm SE) by visit.
SAFETY ANALYSES					
Hypoglycemia	Safety	Follow safety guidelines Number (%) of patients with any investigator reported hypoglycemia, severe hypoglycemia, documented symptomatic hypoglycemia during TEAE period, and incidence rates in 100 patient-years.		Severe hypoglycemia or documented symptomatic hypoglycemia by subgroups: race, age group, gender	Severe hypoglycemia or documented symptomatic hypoglycemia: frequency summary of first event / recurrent event by weekly time intervals; frequency summary of any event by hour; KM plot time to first event Documented symptomatic hypoglycemia maybe presented by <54 mg/dL (3.0 mmol/L) as appropriate.
Adverse events	Safety	Follow safety guidelines	No	Common TEAEs by subgroups: race, age, gender, baseline SBP, baseline eGFR	
Clinical laboratory data	Safety	Follow safety guidelines	Descriptive	No	No
Vital signs	Safety	Follow safety guidelines	Descriptive	No	No
ECG, Physical examination	Safety	Follow safety guidelines	Frequency summary	No	No

ITT = intent-to-treat; ANCOVA = analysis of covariance

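### Adverse event terms that only one sex can have are divided by treated patients of both sexes, and no summary of genital mycotic infection by sex is assured

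*Protocol*

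**What the plan says.** Both documents fix the denominator of the adverse event incidence tables in the same words: "The denominator for computation of percentages is the safety population within each treatment group" (Protocol Section 11.4.3.2, All adverse events; SAP Section 2.4.5.3, Generalities). Neither exempts terms that only one sex can have.

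Protocol Section 4.6 says that "genital infections are monitored closely as an important identified risk", and describes the other class effects as potential risks. Genital mycotic infection is an event of special interest (EOSI), and its definition in Protocol Section 10.4.1.4 names one female and one male infection. The analysis does not follow that division. The protocol says "The number (n) and percentage (%) of patients with each EOSI event will be summarized by treatment group" (Section 11.4.3.4). For non-adjudicated EOSIs the SAP says "the number (%) of patients with at least one event will be summarized by treatment group and by PT" (Section 2.4.5.3, Other EOSIs).

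A split by sex is planned elsewhere. SAP Section 2.4.5.3 says that a table of common events, meaning PTs with incidence of 2% or more in any treatment group, "will be provided as appropriate by primary SOC and PT and by demographic factors including gender". Appendix C lists it as "Common TEAEs by subgroups: race, age, gender, baseline SBP, baseline eGFR". SAP Section 2.4.5 adds: "Selected safety analyses will be summarized by age, gender, racial subgroups, and any pertinent subgroups". It refers for details to Sections 2.4.5.3 and 2.4.5.4; the first contains the conditional table just described, and the second, on deaths, has no split by gender.

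**The concern.** For a term such as vulvovaginal candidiasis or fungal balanitis, the rule counts patients who cannot have the event. The printed percentage is then not the risk in anyone who can have it, and the absolute difference from placebo shrinks by the same proportion.

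This matters most for genital infection, because it is the harm that the protocol itself names as an important identified risk. A prescriber wants the absolute excess risk for a woman and for a man. As planned, the one-sex rows give a diluted figure, the EOSI row pools the sexes, and the by-gender table depends on a screen that itself uses the diluted figure. The SAP does plan a by-gender summary for severe or documented symptomatic hypoglycemia (Section 2.4.5.2), so the missing one for genital infection looks like an oversight.

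**Working it through.** The plan states no adverse event rate, sex ratio or sex-specific denominator, so there is no figure of its own to reproduce.

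**Inputs**
- Arm size: 120 (SAP Section 1.1), taken here as the number treated.
- Genital mycotic PTs (SAP Appendix B): 8. Three are female-only (vulvovaginal candidiasis, vulvovaginal mycotic infection, candida cervicitis), two are male-only (balanitis candida, fungal balanitis), and three can occur in either sex.
- By-gender screen: 2% in any arm. Since 0.02 × 120 = 2.4, it takes 3 patients (3/120 = 2.5%; 2/120 = 1.7% fails).
- Share of women, f: not in the documents; 40% to 60% is assumed.

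**Dilution.** For a female-only term, printed % = (% among women) × f. For a male-only term the factor is 1 − f. The risk difference is multiplied by the same factor. The factor cancels from the risk ratio when f is equal across arms, which stratification by sex makes nearly true.

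| Women in arm | Factor, female terms | Factor, male terms | 12 women with the event: printed | Same, among women | Screen (3 patients) as % of women |
|---|---|---|---|---|---|
| 48 (40%) | 0.4 | 0.6 | 10% | 25.0% | 6.3% |
| 60 (50%) | 0.5 | 0.5 | 10% | 20.0% | 5.0% |
| 72 (60%) | 0.6 | 0.4 | 10% | 16.7% | 4.2% |

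With 30% to 70% women the factor would run from 0.3 to 0.7.

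**Risk difference and ratio.** Assume 10% versus 2% among women and f = 0.5. The all-patient row shows 5.0% versus 1.0%. The difference falls from 8 to 4 percentage points; the ratio is 5.0 either way.

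**Pooled EOSI row.** Printed % = f × (% in women) + (1 − f) × (% in men). Assume 20% in women, 4% in men and f = 0.5: 0.5 × 20 + 0.5 × 4 = 12%. That is right for all patients, too low for women and too high for men.

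**Does the by-gender table catch it?** Take 60 women per arm and a true risk r for one female-only term in both active arms. With q = P(Binomial(60, r) ≥ 3), the chance that at least one active arm passes the screen is 1 − (1 − q)².
- r = 3%: q = 0.269, chance 0.465.
- r = 5%: q = 0.583, chance 0.826.
- r = 10%: q = 0.947, chance 0.997.

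So a single frequent term will almost surely appear, including the 12-of-120 case above.

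**Where it fails.** Suppose each of the three female-only terms occurs in 2 different women in an arm and no term reaches 3 in any arm. Then 3 × 2 = 6 women are affected: 6/48 = 12.5%, 6/60 = 10.0% or 6/72 = 8.3% of women. Each PT row prints 1.7%, no by-gender row is triggered, and with no other cases the pooled EOSI row prints 6/120 = 5.0%.

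**The case against.** The strongest reply is that little is lost.
- Both sexes can have a genital mycotic infection, so the full safety population is a proper denominator for the EOSI.
- The EOSI summary is by PT, so female-only and male-only terms already sit on separate rows.
- Frequent terms reach the by-gender table, where a percentage would normally use patients of that gender, though the SAP does not say so.
- Gender is tabulated by arm and appears in the adverse event listings, so a reader could divide by hand.
- Randomization is stratified by sex, relative risk is the comparative measure that the SAP mentions for safety data, and safety endpoints are not formally tested.

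Most of this stands, and it limits the point. It does not close the gap. The by-gender table is discretionary and screened on both sexes, and it never shows the EOSI as a group. Hand repair is imperfect: adding PT rows can count a patient twice, the three terms open to both sexes do not reveal sex, and demographics are tabulated on the randomized population (SAP Section 2.4.1), not the safety population.

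A reader might go further and infer that the identified risk itself will be reported at about half its true size. The documents do not support that. They give no sex mix, so one half is only the value at an even split, and the dilution applies to one-sex PT rows, not to the pooled EOSI. Nor do they support saying that risk by sex cannot be read from any planned table, or that the comparison between arms is distorted on the ratio scale.

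**Conclusion.** The point holds as a limited reporting gap. For one-sex PTs the stated rule prints absolute risks and risk differences at 0.4 to 0.6 of their sex-specific values, on the assumption that each sex makes up 40% to 60% of an arm. The pooled genital mycotic infection figure is valid but can hide a difference between women and men. The by-gender table usually covers frequent terms. It can miss several less frequent ones that together affect, in the constructed example, 8.3% to 12.5% of women. That example shows what the rule permits; it is not a forecast. Because this is the harm singled out in Protocol Section 4.6 and the remedy is nearly free, the change is worth making.

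**What to change.** In SAP Section 2.4.5.3:
1. State that percentages for PTs that only one sex can have use the safety-population patients of that sex in the arm as denominator, and that the 2% screen for those PTs does the same.
2. Apply the same denominator to male-only EOSIs such as prostate cancer. Do not apply it to the Leydig-cell grouping as a whole, because SAP Table 2 includes an ovarian term in it.
3. Report n (%) of patients with any genital mycotic infection separately for women and men by arm, whatever the incidence, beside the pooled row.

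The protocol carries the same denominator sentence, so the exception should be recorded in the table of changes in SAP Section 1.6.

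The cost is a few lines of text and one or two extra rows or tables; sex is already recorded and is a stratification factor. Denominators per cell become smaller, so percentages will be less stable. The screen also becomes easier to pass: 2% of 48 is 0.96, so 1 patient suffices, while 2% of 60 is 1.2 and of 72 is 1.44, so 2 patients suffice.
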